From AE data reported following LOXO-305 administration in healthy volunteers in the LOXO-BTK-20014 study, all TEAEs (headache, nausea, and vomiting) were Grade 1 in severity and considered related to LOXO-305. All 3 events were reported by 1 subject and resolved within 1 to 1.5 days (data on file at the time of protocol development). From preliminary AE data reported following LOXO-305 administration in healthy volunteers in the LOXO-BTK-20006 study, all TEAEs (intermittent belching, bloating, insect bite, aphthous ulcer, nausea, intermittent diarrhea [x2], muscle twitch) were Grade 1 in severity and bloating, intermittent diarrhea and intermittent belching were considered related to LOXO-305. All 7 AEs were reported by 3 subjects and all events resolved prior to End of Treatment (EOT; data on file at the time of protocol development). From preliminary AE data reported following LOXO-305 administration in healthy volunteers in Cohort 1 of the LOXO-BTK-20017 study, there was one TEAE (headache), observed in the 300 mg LOXO-305 Cohort ,which was Grade 1 in severity and considered related to LOXO-305. The event resolved within 2 hours (data on file at the time of protocol development).

To date, there have been no clinically significant abnormal findings in vital signs and ECG data in the studies investigating LOXO-305 conducted in healthy volunteers.

In healthy volunteers, the geometric mean single-dose C_{max} of approximately 5450 ng/mL following a 200-mg single dose is column below the NOEL (in rat, column) for micronuclei induction.

1.5. Study Rationale

Liver disease can cause alterations in drug disposition and PK. Such alterations can reduce the clearance of drugs eliminated by hepatic metabolism or biliary excretion and affect plasma protein binding, which in turn could influence the processes of absorption, distribution, and elimination. Results from this study will provide information on the safety, tolerability, and exposure of LOXO-305 in participants with hepatic impairment and participants with normal hepatic function.

This study is being conducted to provide information to develop dosing recommendations for LOXO-305 in subjects with hepatic impairment. The current study will be carried out in subjects with hepatic impairment according to 3 different Child-Pugh (CP) categories^{9,10} (mild, moderate, and severe impairment) and also in matched-control healthy subjects. Of these hepatic impairment subjects enrolled per CP category, enrollment will also aim to have at least 4 subjects meet severe hepatic impairment criteria per National Cancer Institute's Organ Dysfunction Working Group (NCI-ODWG) classification, at least 4 subjects meet moderate hepatic impairment criteria per NCI-ODWG classification, and at least 4 subjects meet mild hepatic impairment criteria per NCI-ODWG classification. ¹¹

There are several methods used to categorize the severity of hepatic impairment. Despite its imperfections, the CP classification is the most widely used and is an acceptable method supported by regulatory agencies (including the United States Food and Drug Administration [FDA] and the European Medicines Agency [EMA]). Further data analysis will be performed using NCI-ODWG classification for hepatic dysfunction (see Section 8).¹¹ The FDA and EMA Guidelines recommend that the "number of subjects enrolled should be sufficient to detect clinically relevant PK differences." In the current study, up to 8 subjects with mild

hepatic impairment, up to 8 subjects with moderate hepatic impairment, up to 8 subjects with severe hepatic impairment, and 8 to 24 healthy subjects with normal hepatic function will be enrolled. The PK and safety profiles between each hepatic impairment group and their matching (age, sex, and body mass index [BMI]) healthy subjects will be compared.

1.6. Risk Assessment

Subjects in the current study will not receive any health benefit (beyond that of an assessment of their medical status) from participating in the study. The risks of participation are primarily those associated with adverse reactions to the study treatments, although there may also be some discomfort from collection of blood samples and other study procedures. More information about the known and expected benefits, risks, and reasonably anticipated AEs associated with LOXO-305 may be found in the IB. ¹

Single doses of 200 mg LOXO-305 were investigated in a study conducted in healthy volunteers (LOXO-BTK-20014) where 10 healthy volunteers were given 200 mg of LOXO-305 on 3 separate days, each followed by a washout period. Two additional studies are ongoing in healthy volunteers (LOXO-BTK-20006 and LOXO-BTK-20017). LOXO-BTK-20006 is a drug-drug interaction study evaluating the effects of a strong CYP3A4 inhibitor (itraconazole) and a strong CYP3A4 inducer (rifampin) on the PK of LOXO-305 where, at the time of protocol development, 6 healthy volunteers were given 1 dose of 200 mg of LOXO-305, 12 healthy volunteers were given 200 mg of LOXO-305 on 2 separate days (1 of which was co-administered with itraconazole), each followed by a washout period, and 9 healthy volunteers were given 200 mg of LOXO-305 on 3 separate days (2 of which were co-administered with rifampin), each followed by a washout period. LOXO-BTK-20017 is a single ascending dose study evaluating the safety and tolerability of LOXO-305 at 300 mg, up to 600 mg, up to 800 mg, and up to 900 mg (if necessary) where, at the time of protocol development 6 healthy volunteers were given a single dose of 300 mg LOXO-305 and 6 healthy volunteers were given a single dose of 600 mg LOXO-305.

From AE data reported following LOXO-305 administration in 10 healthy volunteers in the LOXO-BTK-20014 study, all TEAEs (headache, nausea, and vomiting) were Grade 1 in severity and considered related to LOXO-305. All 3 events were reported by 1 subject and resolved within 1 to 1.5 days (data on file at the time of protocol development). From preliminary AE data reported following LOXO-305 administration in healthy volunteers in the LOXO-BTK-20006 study, all TEAEs (intermittent belching, bloating, insect bite, aphthous ulcer, nausea, intermittent diarrhea [x2], muscle twitch) were Grade 1 in severity and bloating, intermittent diarrhea and intermittent belching were considered related to LOXO-305. All 7 AEs were reported by 3 subjects and all events resolved prior to EOT; data on file at the time of protocol development). From preliminary AE data reported following LOXO-305 administration in healthy volunteers in Cohort 1 of the LOXO-BTK-20017 study, there was one TEAE (headache) observed in the 300 mg LOXO-305 Cohort which was Grade 1 in severity and considered related to LOXO-305. The event resolved within 2 hours (data on file at the time of protocol development).

The safety monitoring practices employed will include AE reporting, vital sign measurements, 12-lead electrocardiogram (ECG), clinical laboratory evaluations, and physical examinations, and are considered adequate to protect the subjects' safety.

2. OBJECTIVES AND ENDPOINTS

2.1. Objectives

2.1.1. Primary Objective

The primary objective of the study is to evaluate the PK profile of LOXO-305 in subjects with impaired hepatic function compared to matched-control healthy subjects.

2.1.2. Secondary Objective

The secondary objective of the study is to evaluate safety and tolerability of LOXO-305 in subjects with impaired hepatic function and matched-control healthy subjects.

2.2. Endpoints

2.2.1. Primary Endpoints

The following PK parameters will be calculated whenever possible, based on the plasma concentrations of LOXO-305:

- C_{max}
- \bullet t_{max}
- area under the concentration-time curve (AUC) from hour 0 to the last measurable concentration (AUC_{0-t})
- AUC from hour 0 extrapolated to infinity (AUC_{0-inf})
- percentage extrapolation for AUC_{0-inf} (%AUC_{extrap})
- apparent terminal elimination rate constant (λ_z)
- apparent plasma terminal elimination half-life ($t_{1/2}$)
- apparent systemic clearance (CL/F)
- apparent volume of distribution during the terminal phase (V_z/F)
- mean residence time (MRT).

In addition, a single blood sample will be collected predose to determine the fraction unbound (f_u) of LOXO-305 in plasma and, whenever possible, the following PK parameters will be calculated for unbound LOXO-305 using f_u : unbound C_{max} ($C_{max,u}$), unbound AUC_{0-tr} (AUC_{0-tr}), unbound AUC_{0-inf} (AUC_{0-inf},u), unbound CL/F (CL/F,u), and unbound V_z /F (V_z /F,u).

2.2.2. Secondary Endpoints

Safety and tolerability will be assessed by monitoring AEs, performing physical examinations and clinical laboratory evaluations, measuring vital signs, and recording ECGs.

3. INVESTIGATIONAL PLAN

3.1. Overall Study Design and Plan

This study is an open-label, nonrandomized, multi-center, single-dose, parallel-group study to determine the PK, safety, and tolerability of LOXO-305 administered orally at a dose of 200 mg to fasted adult males and females with mild, moderate, or severe impaired hepatic function and healthy subjects with normal hepatic function. Hepatic function will be classified based on the CP classification of hepatic impairment (Table 3).^{9,10}

Subjects will be recruited in this study so that up to 24 subjects with hepatic impairment (up to 8 subjects with mild impairment, up to 8 subjects with moderate impairment, and up to 8 subjects with severe impairment, per CP classification – assessed at Screening and verified at Check-in [Day -1]) and 8 to 24 subjects with normal hepatic function are enrolled, with the goal of having at least 6 subjects from each hepatic impairment group per CP classification and at least 6 subjects with normal hepatic function complete the study. Hepatically impaired subjects will be assigned to groups according to CP scores at Check-in (Day -1) to ensure stability of hepatic impairment and subject safety, as determined by the Investigator [or designee]. Subjects will be enrolled within the following groups based on their CP score at Screening and Check-in (Day -1) as judged by the Investigator (or designee), Covance Medical Monitor, and Sponsor:

- Group 1: Matched-control healthy subjects with normal hepatic function;
- Group 2: Subjects with mild hepatic impairment (CP Class A, score of 5 or 6);
- Group 3: Subjects with moderate hepatic impairment (CP Class B, score of 7 to 9);
- Group 4: Subjects with severe hepatic impairment (CP Class C, score of 10 to 15).

A parallel-design strategy will be adopted for the hepatic impairment groups, with interim reviews (as detailed in Section 8.2) of the safety data after the first 2 subjects from Group 2 (mild hepatic impairment subjects) and Group 3 (moderate hepatic impairment subjects) and matched-control healthy subjects are enrolled and have completed all study-related assessments including the follow-up phone call.

Each matched-control healthy subject (Group 1) will be demographically matched (1:1) by age (\pm 10 years), BMI (\pm 20%), and sex to the completed hepatic impairment subject(s). Should another hepatic impairment subject be identified with whom an already enrolled healthy subject is demographically matched, the healthy subject may also be matched with that impaired subject as long as the impaired subject is in a different hepatic impairment group. Each subject with normal hepatic function may be matched with up to 1 subject within each hepatic impairment group.

[figure not shown]
The schematic of the study design is displayed in Figure 2. The start of the study is defined as the date the first subject who is enrolled in the study signs an Informed Consent Form (ICF). Note that enrolled subjects are defined as those subjects who are assigned a dose of study drug; this definition excludes screen failure subjects. Replacement subjects may be enrolled only if deemed necessary by the Sponsor.

To assess their eligibility to enter the study, potential subjects will be screened within 28 days (Days -29 to -2) and admitted to the Clinical Research Unit (CRU) on Day -1 (Check-in). Subjects who are determined to be screen failures are permitted to be re-screened if the Investigator (or designee), with agreement from the Covance Medical Monitor and the Sponsor, feels that the subject may meet eligibility criteria upon re-screen. Re-screened subjects will be provided a new subject number.

Subjects will be confined at the CRU from the time of Check-in (Day -1) until EOT on Day 8 upon completion of all PK and safety assessments or Early Termination (ET) if the subject discontinues. A follow-up phone call will occur for all subjects who received a dose of study drug (including subjects who are terminated early) 7 days (\pm 2 days) after EOT or ET. The duration of participation is expected to be approximately 46 days (Screening through follow-up phone call).

On the morning of Day 1, after at least an 8-hour fast, a single oral dose of 200 mg LOXO-305 will be administered with 240 mL of water. No food will be allowed for up to 2 hours postdose. Glucose tablets may be administered as needed for treatment of hypoglycemia. For instructions regarding food and water intake, refer to Section 6.2. Pharmacokinetic samples will be obtained through 168 hours postdose.

Figure 2: Study Design Schematic

ICF = Informed Consent Form; PK = pharmacokinetic.

Note: Single oral dose of LOXO-305 at 200 mg administered orally after at least an 8-hour fast.

In this study, physical examinations, 12-lead ECGs, vital sign measurements, How Do You Feel? (HDYF?) inquiries, clinical chemistry panel, coagulation parameters, hematology panel, urinalysis (UA; Appendix 2), and recording of concomitant medications will be performed at specified times during the study (for specific timepoints and details on each study variable, refer to Appendix 4).

Adverse events and serious AEs (SAEs) will be collected beginning at informed consent. Adverse events will be reported throughout the study (ie, from signing of the ICF until End of Study [EOS], or until ET if the subject discontinues from the study and does not complete a follow-up phone call), either as subject medical history (if the event is reported as beginning prior to signing of the ICF or if the event occurs prior to study drug administration on Day 1 and is assessed as not related to study procedures by the Investigator [or designee]) or as AEs (if the event occurs after signing of the ICF but prior to study drug administration on Day 1 and is assessed as related to study procedures by the Investigator [or designee], or if the event occurs after study drug administration on Day 1 through EOT or ET regardless of relationship

to study drug). From EOT or ET through EOS, only AEs assessed as related to study drug by the Investigator (or designee) are to be reported. All SAEs that develop from the time of ICF signing until EOS (or ET, if the subject discontinues from the study and does not complete a follow-up phone call) are to be reported.

A Schedule of Assessments is presented in Appendix 4. Study completion is defined as the time of the last subject's follow-up.

3.2. Child-Pugh Classification

Per FDA Guidance¹² hepatic impairment will be classified as mild, moderate, or severe using the CP System (Table 3),^{9,10} and the parameters to determine the CP class for each subject with hepatic impairment will be collected at Screening and Check-in (Day -1). Further data analysis will be performed using NCI-ODWG classification (see Section 8).

Table 3: Child-Pugh Assessment of Hepatic Function

	Points Scored for Observed Findings		
	1	2	3
Hepatic encephalopathy grade ^a	0	1 or 2°	3 or 4°
Ascites ^b	Absent	Slight	Moderate
Serum bilirubin, mg/dL (μmol/L)	< 2 (< 34)	2 to 3 (34 to 50)	> 3 (> 50)
Serum albumin, g/dL (g/L)	> 3.5 (> 35)	2.8 to 3.5 (28 to 35)	< 2.8 (< 28)
International normalized ratio	< 1.7	1.7 to 2.3	> 2.3

Chronic Hepatic Impairment is classified into Child-Pugh (CP) class A to C, employing the added score of the 5 parameters in the table above.

Mild Impairment (CP-A): 5 or 6 points; Moderate Impairment (CP-B): 7 to 9 points; Severe Impairment (CP-C): 10 to 15 points.

^a In this study, hepatic encephalopathy is graded according to the following criteria:

- Grade 0: normal consciousness, personality, neurological examination, or normal electroencephalogram;
- Grade 1: restless, sleep disturbed, irritable/agitated, tremor, impaired handwriting, or 5 cycles per second waves;
- Grade 2: lethargic, time-disoriented, inappropriate, asterixis, ataxia, or slow triphasic waves;
- Grade 3: somnolent, stuporous, place-disoriented, hyperactive reflexes, rigidity, or slower waves;
- Grade 4: unarousable coma, no personality/behavior, decerebrate, or slow 2 to 3 cycles per second delta activity.

- Absent: No ascites is detectable by manual examination or by ultrasound investigation, if ultrasound investigation is performed;
- Slight: Ascites palpitation doubtful, but ascites measurable by ultrasound investigation, if performed;
- Moderate: Ascites detectable by palpitation and by ultrasound investigation, if performed;
- Severe: Necessity of paracentesis; does not respond to medication treatment.

3.3. NCI-ODWG Classification

Subjects will also be classified according to NCI-ODWG criteria (Table 4).¹¹ Of these hepatic impairment subjects enrolled per CP classification, enrollment will also aim to have at least 4 subjects meet severe hepatic impairment criteria per NCI-ODWG classification, at least 4 subjects meet moderate hepatic impairment criteria per NCI-ODWG classification, and at least 4 subjects meet mild hepatic impairment criteria per NCI-ODWG classification.

^b Ascites is graded according to the following criteria:

^c A subject with hepatic encephalopathy of Grade 2 or above would not be admitted into the study.

Table 4: National Cancer Institute-Organ Dysfunction Working Group for Hepatic Dysfunction Criteria

	NCI-ODWG (Criteria Cri
Hepatic Impairment	Total Bilirubin	AST
Normal	≤ULN	≤ULN
Mild	> ULN to 1.5 x ULN	>ULN
Moderate	>1.5 to 3 x ULN	Any
Severe	> 3 - 10 x ULN	Any

Abbreviations: AST = aspartate aminotransferase; NCI-ODWG = National Cancer Institute-Organ Dysfunction Working Group; ULN = upper limit of normal.

3.4. Discussion of Study Design

A single-dose, parallel design is the standard design to investigate the PK of a drug in subjects with hepatic impairment. A parallel design is required to include subjects with hepatic impairment and matched-control healthy subjects with normal hepatic function. A single dose level of LOXO-305 will be used because it is the dose intended for registration. The study will be open label because the primary endpoints are objective rather than subjective.

Matched-control healthy subjects with normal hepatic function will be enrolled in this study to serve as a reference group for interpretation of the results. Patients with a range of hepatic impairment will be included to enhance the ability to detect and characterize the effects of hepatic function on the PK of LOXO-305. Based on nonclinical and clinical data, and the known PK profile of the compound, the duration of the treatment period is considered adequate to achieve the study objectives. Oral doses were chosen because this is the intended clinical route of administration.

Preclinical and clinical data suggest that LOXO-305 is likely to be well tolerated in healthy human subjects. However, liver disease can cause alterations in drug disposition, reducing the clearance of drugs eliminated by hepatic metabolism or biliary excretion and affect plasma protein binding, which in turn could influence the processes of distribution and elimination. Therefore, in this study, a cautious approach will be adopted, where the first 2 subjects from Group 2 (mild hepatic impairment subjects) and Group 3 (moderate hepatic impairment subjects) and matched-control healthy subjects may be dosed concurrently, followed by an interim review of the safety and PK data (if available) before dosing is resumed for the remaining subjects in any (all) group(s) (see Section 8.2).

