Subjects will be assigned into groups based on their level of hepatic function (Table 5) and will be assigned a number by CRU staff based on the assigned group. Assignment of numbers within each group will be in ascending order and no numbers will be omitted. Subject number will consist of 6 digits in which the first set of 3 digits will identify the CRU and the second set of 3 digits will identify the subject (eg, 001-101).

Subject numbers will be used on all study documentation.

Group 1: Matched-control healthy subjects: 001-100 through 001-199

Group 2: Subjects with mild hepatic impairment: 001-200 through 001-299

Group 3: Subjects with moderate hepatic impairment: 001-300 through 001-399

Group 4: Subjects with severe hepatic impairment: 001-400 through 001-499.

For subjects who are withdrawn by the Investigator (or designee) or who voluntarily withdraw prematurely from the study, replacement subjects will be enrolled only if deemed necessary by the Sponsor. If necessary, as determined by the Sponsor, subjects who fail to complete the treatment or have insufficient PK data may be replaced. Replacement subjects will be assigned a subject number by adding 400 to the last 3 digits of the subject number for the subject they are replacing (eg, Subject Number 001-501 replaces Subject Number 001-101). Subjects who are determined to be screen failures are permitted to be re-screened if the Investigator (or designee), with agreement from the Covance Medical Monitor and the Sponsor, feels that the subject may meet eligibility criteria upon re-screen. Re-screened subjects will be provided a new subject number as defined above.

Table 5: Subject Group and Number of Subjects

Group	Description of Hepatic Function ^a	N
1	Matched Normal Hepatic Function	8 to 24
2	Mild Hepatic Impairment	8
3	Moderate Hepatic Impairment	8
4	Severe Hepatic Impairment	8

^a Hepatic function determined using the Child-Pugh assessment (Section 3.2).

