5.4. Blinding

This is an open-label study.

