8.5.1.1. Criteria for the Calculation of Apparent Terminal Elimination Rate Constant and Half-life

The start of the terminal elimination phase for each subject will be defined by visual inspection and generally will be the first point at which there is no systematic deviation from the log-linear decline in concentrations.

The apparent terminal elimination rate constant (λ_z) will only be calculated when a reliable estimate can be obtained using at least 3 data points, preferably not including C_{max} , and the adjusted coefficient for determination of exponential fit (R^2 -adj) of the regression line is ≥ 0.7 . Parameters requiring λ_z for their calculation (eg, AUC_{0-inf} , $t_{1/2}$, CL/F , and V_z/F , and MRT_{inf}) will only be calculated if the R^2 -adj value of the regression line is ≥ 0.7 .

The following regression-related diagnostic PK parameters will be determined, when possible:

Parameter	Units	Definition
λ_z	1/h	apparent terminal elimination rate constant
λ_z Upper	h	end of exponential fit
λ_z Lower	h	start of exponential fit
λ_z N	NA	number of data points included in the log-linear regression
λ_z Span Ratio	NA	time period over which λ_z was determined as a ratio of $t_{1/2}$
R^2 -adj	NA	adjusted coefficient for determination of exponential fit

Where possible, the span of time used in the determination of λ_z (ie, the difference between λ_z Upper and λ_z Lower) should be ≥ 2 half-lives. If the λ_z Span Ratio is < 2 , the robustness of the $t_{1/2}$ values will be discussed in the CSR.

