8.5.1.4. Treatment of Outliers in Pharmacokinetic Analysis

If a value is considered to be anomalous due to being inconsistent with the expected PK profile, it may be appropriate to exclude the value from the PK analysis. However, the exclusion of any data must have strong justification and will be documented in the CSR.

Any quantifiable predose concentration value will be considered anomalous and set to missing for the PK analysis.

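### SAP 8.5.1 leaves the terminal-phase choice and value exclusions to judgement while the subject number reveals the hepatic group; masking the group until these are locked is a cheap, low-priority improvement

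*Protocol*

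**What the plan says.** Protocol 5.4 states "This is an open-label study", and protocol 3.4 gives the reason: "The study will be open label because the primary endpoints are objective rather than subjective".

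SAP 8.5.1.1 states: "The start of the terminal elimination phase for each subject will be defined by visual inspection". It adds a criterion: this will generally be the earliest point after which log concentrations show no systematic departure from a straight-line decline. λz "will only be calculated when a reliable estimate can be obtained using at least 3 data points", preferably without Cmax, and with adjusted R² of at least 0.7. The fitted span should reach 2 half-lives where possible. If it does not, the robustness of the half-life "values will be discussed in the CSR"; the estimate is not removed.

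SAP 8.5.1.4 states: "If a value is considered to be anomalous due to being inconsistent with the expected PK profile, it may be appropriate to exclude the value". Any exclusion needs strong justification and must be documented in the CSR.

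Protocol 4.5 numbers healthy subjects in the 100s, mild in the 200s and moderate in the 300s, and continues: "Group 4: Subjects with severe hepatic impairment: 001-400 through 001-499". Replacements add 400 to the number, so they still show the group. These numbers go on all study documentation.

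Neither document masks the PK analyst to hepatic group.

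**The concern.** The SAP leaves two decisions to a person: where a subject's terminal phase starts, and whether a concentration is anomalous. The group is readable from the subject number, and the expectation has a direction, because protocol 1.5 and 3.4 say liver disease can reduce clearance. An analyst who expects slower elimination in impaired subjects could, without meaning to, favour later windows or keep high late concentrations in those subjects.

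Ten of the fifteen listed primary PK parameters use λz in some way, but only a few are sensitive to its choice. At stake is the description of half-life and Vz/F by hepatic group, plus any parameter touched by a discretionary exclusion. The groups are small (at least 6 completers intended in each), so a few choices can show in a group summary.

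**Working it through.** The plan states no figure on this point, so there is nothing to reproduce. The check asks how much room the SAP rules leave.

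**Inputs from the documents.** Sampling runs to 168 h (protocol 3.1), with up to 20 PK samples (protocol Appendix 3). Half-life is about 20 h in cancer patients (protocol 1.4.2). The limits are those of SAP 8.5.1.1. AUC0-inf with more than 30% extrapolated is left out of the analysis (SAP 8.5.1.2).

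**Assumptions.** The sampling times are blacked out, so 19 or 20 plausible times to 168 h were assumed, with log-normal noise of 10% to 20%. Half-lives of 40 h and 60 h stand for possible slowing by impairment; neither is in the documents.

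**Step 1: which parameters depend on the window.**
- Cmax and AUC0-t do not use λz.
- t1/2 = ln 2/λz, so it moves one for one with the choice.
- AUC0-inf = AUC0-t + Ct/λz, so only the extrapolated part moves. For a mono-exponential decline that part is 2^(−168/t1/2): 0.3% at 20 h, 5.4% at 40 h and 14.4% at 60 h.
- CL/F = Dose/AUC0-inf, so it moves as little as AUC0-inf.
- Vz/F = (CL/F)/λz, so it moves almost as much as half-life.
- MRTinf = AUMC0-inf/AUC0-inf (AUMC is the area under the curve of time × concentration). With k = ln 2/t1/2, the mono-exponential extrapolated share of AUMC is e^(−168k)(1 + 168k). At 40 h, 168k = 2.911 and the share is 0.0544 × 3.911 = 21%. At 20 h it is 0.00296 × 6.822 = 2%, and at 60 h 0.1436 × 2.941 = 42%. MRTinf is thus more exposed than AUC0-inf but less than half-life.

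**Step 2: spread of admissible half-lives within one subject.** For each simulated profile, every window ending at the last quantifiable point, with at least 3 points and adjusted R² ≥ 0.7, was fitted. The largest half-life was divided by the smallest. Median spread, with windows starting at or after 24 h:

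| True t1/2 | Span target not applied | Span ≥ 2 half-lives met |
|---|---|---|
| 20 h | about 8% to 17% | little changed (168/20 = 8.4 half-lives sampled) |
| 40 h | 17% to 31% | 7% to 16% |
| 60 h | 25% to 38% | 3% to 9% |

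The fall at 60 h is arithmetic: a span of 120 h ending at 168 h must start by 48 h, so few windows remain. A second run let windows start at any point after Cmax, with 10% noise. It gave 25% at 40 h and 36% at 60 h without the span target, and 19% and 21% with it.

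**Step 3: carry-over to AUC0-inf.** The simulated change was below 0.1% at 20 h, about 1% at 40 h and 3% to 4% at 60 h. A rough check (extrapolated share × half-life spread) gives 0.054 × 0.25 = 1.4% at 40 h and 0.144 × 0.36 = 5.2% at 60 h, the same order.

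**Step 4: carry-over to Vz/F.** In the second run, with 10% noise and no span target, the half-life ratio over the AUC0-inf ratio is 1.252/1.010 = 1.24 at 40 h and 1.361/1.037 = 1.31 at 60 h.

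**Step 5: one subject's weight.** A 1.36-fold choice in one of 6 subjects moves the group geometric mean by 1.36^(1/6) = 1.05, about 5%.

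**Edge case.** At a half-life near 97 h, 2^(−168/97) = 30%. There the window could decide whether a subject's AUC0-inf is analysed. Nothing in the documents suggests half-lives that long.

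**The case against.** The strongest reply is that the SAP already disciplines these choices. It states where the terminal phase should generally start, sets a minimum number of points and fit, and aims for a span of 2 half-lives. It also produces the window limits, number of points, span ratio and adjusted R² as diagnostics. Exclusions need strong justification and CSR documentation, anomalous values are flagged, and all concentrations and parameters are listed. A reader could audit and recalculate. All of this stands, and it is why the point is minor. But these safeguards narrow or document the choice; none hides the group while it is made.

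Four stronger readings are tempting, and the documents do not support them.
- *Protocol 3.4 is wrong.* It explains why treatment is unmasked. Every subject gets the same single 200 mg dose, and assayed concentrations are reasonably called objective. Masking the analyst is a separate matter.
- *The formal comparisons are compromised.* SAP 8.5.3.1 compares AUC0-t, AUC0-inf and Cmax, total and unbound. Two of these do not use λz, and the third barely moves. In the visible text, half-life and Vz/F are only summarised.
- *The ratio of half-lives between groups could be moved by the full spread.* That would need every subject in one group pushed to one extreme and every subject in the other group to the opposite one, against the stated start criterion.
- *The analyst certainly sees the group.* This is inferred from the numbering; no section says which identifiers are in the analysis file.

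**Conclusion.** The point holds as a low-priority, inexpensive safeguard. Window selection and anomalous-value exclusion involve judgement, the group can be read from the subject number, and no masking is planned. The material exposure is λz, half-life and Vz/F, to a lesser degree MRTinf, and anything affected by a discretionary exclusion. Through window choice, AUC0-inf and CL/F are nearly unaffected at the only half-life the documents give, and AUC0-t and Cmax not at all.

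The spreads in the working are upper bounds on discretion. They rest on assumed sampling times, noise and profile shape, and the larger ones on assumed half-lives of 40 h and 60 h. How far the span target reduces them depends on how early a window may start. They are not evidence that bias will occur.

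**What to change.** Add one paragraph to SAP 8.5.1 with three statements:
1. The final noncompartmental analysis is run on a file with recoded subject IDs and without hepatic group, Child-Pugh or NCI-ODWG class.
2. λz windows, chosen by the existing 8.5.1.1 rule, and any anomalous-value exclusions are recorded and locked on that file.
3. Group labels and the matching are attached only afterwards.

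The analysis needs no group label, because the dose is the same for everyone. Limiting this to the final analysis leaves the interim safety reviews, which may use PK data, as planned.

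No change to protocol 3.4 is needed. Nor is there a clear case for replacing the start criterion with the window of highest adjusted R². In simulation at a true 60 h with 20% noise, that rule gave a geometric mean of about 56 h, against 58 to 60 h for the first admissible start.

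The cost is one recoding step and a short delay, with no new data or visits. Masking will be imperfect, because a slow profile can itself suggest impairment.
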